2.4. Statistical Hypotheses / Statistical Analyses

No formal hypotheses will be tested.

For IH and IM oxytocin, summary statistics will be produced separately for IH Oxytocin and IM Oxytocin. Due to sparse PK concentrations, it is not possible to include a formal statistical analysis to compare IH and IM Oxytocin. PK parameters will be derived as data permit. Individual plots, listings and summary tables will be produced for available PK concentration data. Only listings and summary tables will be produced for PK Parameter data.

3. PLANNED ANALYSES: GROUP 1

3.1. Interim Analyses: Group 1

No formal Interim Analysis are planned, however, PK samples will be analysed and preliminary PK parameters derived following completion of approximately 5 women on each treatment group: 400 mcg IH and 10 I.U. IM to women in TSL (Group 1) and 400 mcg IH to non-pregnant women on the combined oral contraceptive (Group 2 Cohort A), in order to assess if dose escalation is required.

Due to sparse PK concentration-time data available following administration of IH and IM oxytocin to women in TSL, only concentration time plots were presented at the interim analysis. The Study has been terminated early due the unanticipated inability to be able to quantify plasma oxytocin using a selective and sensitive (LLQ 2pg/mL) analytical assay due to low oxytocin concentrations (<2pg/mL) in the majority of samples collected from women in Third Stage Labour (TSL), following either IM or IH administration. Therefore, the Primary objective of the study to characterise the PK of single doses of IH and IM oxytocin in women in TSL, cannot be met, and the study is being terminated

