7.3. Other Safety Analyses

The analyses of non-laboratory safety test results including ECGs and vital signs will be based on GSK Core Data Standards, unless otherwise specified. The details of the planned displays are presented in [Appendix 10: List of Data Displays](#).

8. PHARMACOKINETIC ANALYSES : GROUP 1

8.1. Primary Pharmacokinetic Analyses : Group 1

8.1.1. Endpoint / Variables : Group 1

- Plasma concentration time profile for IH oxytocin and 10 I.U. IM oxytocin.
- PK parameters: Maximum observed plasma concentration (C_{max}), Observed plasma concentrations at 10 minutes (min) postdose (C_{p10}), Observed plasma concentrations at 20 min post-dose (C_{p20}), Observed plasma concentrations at 30 min post-dose (C_{p30}), Time to C_{max} (t_{max}), Area under concentration-time curve (AUC(0-t)), and time of last quantifiable concentration will be calculated as data permit.

8.1.1.1. Drug Concentration Measures : Group 1

Refer to [Appendix 5: Data Display Standards & Handling Conventions](#) (Section [10.5.2](#) and Section [10.5.3](#) Reporting Standards for Pharmacokinetic)

8.1.1.2. Derived Pharmacokinetic Parameters: Group 1

Pharmacokinetic parameters will be calculated by standard non-compartmental analysis according to current working practices and GSK procedures using the currently supported version of WinNonlin. All calculations of non-compartmental parameters will be based on actual sampling times. Pharmacokinetic parameters listed will be determined from the plasma concentration-time data, as data permits.

Treatment	Parameter	Parameter Description
IH/IM	C _{max}	Maximum observed concentration, determined directly from the concentration-time data.
IH/IM	C _{p10}	Quantified concentration in PK sample collected at 10 minutes (nominal time) post-dose, determined directly from the concentration-time data.
IH/IM	C _{p20}	Quantified concentration in PK sample collected at 20 minutes (nominal time) post-dose, determined directly from the concentration-time data.
IH/IM	C _{p30}	Quantified concentration in PK sample collected at 30 minutes (nominal time) post-dose, determined directly from the concentration-time data.
IH/IM	t _{max}	Time to reach C _{max} , determined directly from the concentration-time data.

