10.5.2. Reporting Standards

General	

 The current GSK Integrated Data Standards Library (IDSL) will be applied for reporting, unless otherwise stated (IDSL Standards Location: https://spope.gsk.com/sites/IDSLLibrary/SitePages/Home.aspx): 
 4.03 to 4.23: General Principles 5.01 to 5.08: Principles Related to Data Listings 6.01 to 6.11: Principles Related to Summary Tables 7.01 to 7.13: Principles Related to Graphics 	
Formats	

 All data will be reported according to the actual treatment the subject received unless otherwise stated. GSK IDSL Statistical Principles (5.03 & 6.06.3) for decimal places (DP's) will be adopted for reporting of data based on the raw data collected, unless otherwise stated. Numeric data will be reported at the precision collected on the eCRF. The reported precision from non eCRF sources will follow the IDSL statistical principles but may be adjusted to a clinically interpretable number of DP's. 	
Planned and Actual Time	

 Reporting for tables, figures and formal statistical analyses: 
 Planned time relative to dosing will be used in figures, summaries, statistical analyses and calculation of any derived parameters, unless otherwise stated. The impact of any major deviation from the planned assessment times and/or scheduled visit days on the analyses and interpretation of the results will be assessed as appropriate. Reporting for Data Listings: 
 Planned and actual time relative to study drug dosing will be shown in listings (Refer to IDSL Statistical Principle 5.05.1). Unscheduled or unplanned readings will be presented within the subject's listings. 	
Unscheduled Visits	

 Unscheduled visits will not be included in summary tables and/or figures. All unscheduled visits will be included in listings. 	

Descriptive Summary Statistics	
Continuous Data	Refer to IDSL Statistical Principle 6.06.1
Categorical Data	N, n, frequency, %
Reporting of Pharmacokinetic Concentration Data	
Descriptive Summary Statistics	Refer to IDSL Statistical Principle 6.06.1 Assign zero to NQ values (Refer to GUI_51487 for further details)
Reporting of Pharmacokinetic Parameters	
Summary table	Summary table will be produced as described in Section 8.1.2
Listing	All PK Parameters that are collected will be listed

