10.5.3. Reporting Standards for Pharmacokinetic

Pharmacokinetic Concentration Data	
PC Windows Non-Linear (WNL) File	WNL file will be produced for PK parameters. Note: Concentration values will be imputed as per GUI_51487
Descriptive Summary Statistics, Graphical Displays and Listings	Refer to IDSL PK Display Standards. Refer to IDSL Statistical Principle 6.06.1. Note: Concentration values will be imputed as per GUI_51487 for descriptive summary statistics/analysis and summarized graphical displays only.
NONMEM/Pop PK File	Pop-PK file (CSV format) for the POP-PK analysis by Clinical Pharmacology Modelling and Simulation function will be created according to the data specification detailed in Section 9.1 Data Specification of the Pop-PK RAP (RAP-IVF116828-201558-205920-PopPK, located in Cabinets/Study File/GR121619/_Project/Meta Analysis/ RAP-IVF116828-201558-205920-PopPK)
Pharmacokinetic Parameter Derivation	
PK Parameter to be Derived by Programmer	The following PK parameters will be derived by the Programmer: Cp10, Cp20 and Cp30

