10.10.5. Pharmacokinetic Tables

Pharmacokinetic Tables					
No.	Population	IDSL / Example Shell	Title	Programming Notes	Deliverable [Priority]
PK Concentration Data					
2.6.	PK	pkct1	Summary of Plasma Concentration-time Data	Page by subjects before study restart, subjects after restart and all subjects together.	SAC
2.7.	PK	PK_T1	Summary of Derived Plasma Pharmacokinetic Parameters (untransformed data)	Page by subjects before study restart, subjects after restart and all subjects together. This will be an overall summary and will not be displayed by timepoints.	SAC
2.8.	PK	PK_T2	Summary of Number and Percentage of Subjects with Measurable Concentrations	Page by subjects before study restart, subjects after restart and all subjects together. This will be an overall summary and will not be displayed by timepoints.	SAC

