10.10.6. Pharmacokinetic Figures

Pharmacokinetic Figures					
No.	Population	IDSL / Example Shell	Title	Programming Notes	Deliverable [Priority]
Individual Concentration Plots					
2.8.	PK	pkcf6	Individual Subject Plasma Concentration-time Plot (Linear and Semi-log) by Treatment	By Treatment, Page by subjects before study restart, subjects after restart and all subjects together	SAC

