10.11. Appendix 11: Mock Shell

Example: SAFE_T1
Protocol: 205920
Population: Safety

Table x.xx
Summary of Device Acceptability Questionnaire for Rotahaler Inhaler

	Total (N=XX)

Feel Confident Received the Medicine	
n	xx
Yes	xx (xx%)
No	xx (xx%)
Neutral	xx (xx%)
Decline to Answer	xx (xx%)
Find This Inhaler Easy to Use	
n	xx
Yes	xx (xx%)
No	xx (xx%)
Neutral	xx (xx%)
Decline to Answer	xx (xx%)
Prefer Inhaler Instead of Injection	
n	xx
Yes	xx (xx%)
No	xx (xx%)
Neutral	xx (xx%)
Decline to Answer	xx (xx%)

Example: SAFE_T1
Protocol: 205920
Population: Safety

Table x.xx
Summary of Device Acceptability Questionnaire for Rotahaler Inhaler

	Total (N=XX)

This Inhaler Acceptable to Administer	
n	xx
Yes	xx (xx%)
No	xx (xx%)
Neutral	xx (xx%)
Decline to Answer	xx (xx%)

Example : SAFE_L1
Protocol : GR121619
Population : Safety

Page 1 of n

Listing SAFE_T1
Listing of Device Acceptability Questionnaire for Rotahaler Inhaler

Site Id./ Subj Id.	Visit	Date	Question	Response
Xxxx/PPD	PERIOD 1 GRP1	PPD	Feel Confident Received the Medicine	Yes
			Find This Inhaler Easy to Use	Yes
			Prefer Inhaler Instead of Injection	Yes
			This Inhaler Acceptable to Administer	Yes
Xxxx/PPD	PERIOD 1 GRP1	PPD	Feel Confident Received the Medicine	Neutral
			Find This Inhaler Easy to Use	Yes
			Prefer Inhaler Instead of Injection	Yes
			This Inhaler Acceptable to Administer	Yes

Example: PK_T1
Population: Pharmacokinetic {Group}

Table x.x
Summary of Derived [Analyte] [Matrix] Pharmacokinetic Parameters {by Group}

Parameter	Treatment	N	n	n*	Median	Range
AUC(0-t) (units)	400mcg	24	24 24	xxxx.xx xxxx.xx	NC xxxx.xx	NC to NC NC to xx
	17mg	24	24 23	xxxx.xx xxxx.xx	xxxx.xx xxxx.xx	xxxx.x xxxx.x
Cmax (units)	400mcg	24	24 23	xxxx.xx xxxx.xx	xxxx.xx xxxx.xx	xxxx.x xxxx.x
	17mg	24	24 21	xxxx.xx xxxx.xx	xxxx.xx xxxx.xx	xxxx.x xxxx.x

NC = non calculable due to NQ concentrations

NA = not applicable due to insufficient data to derive summary measure

n = Number of subjects with non-missing observations (including imputed NC values)

n* = Number of subjects for whom parameter cannot be derived because of NQ concentrations

Note: for Cmax and AUC, NCs were imputed prior to derivation of summary statistics; No NC values were imputed for tmax.

Cmax imputed with ½ LLQ (5 pg/mL)

AUC(0-t) imputed with ½ lowest observed AUC(0-t) (5.45 pg.h/mL)

Example: PK_T2
Population: Pharmacokinetic

Table x.x
Summary of Number and Percentage of Subjects with Measurable Concentrations

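### Group 1 Table 2.6 sets non-quantifiable oxytocin concentrations to zero although most samples are below the 2 pg/mL LLQ, so its means are biased downward and its medians can print as 0

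*SAP*

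**What the plan says.** All references are to the Group 1 RAP unless stated.

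- **Rule.** Section 10.5.2, on reporting concentration data: "Assign zero to NQ values (Refer to GUI_51487 for further details".
- **Reach.** Section 10.5.3: "Concentration values will be imputed as per GUI_51487 for descriptive summary statistics/analysis and summarized graphical displays only".
- **Extent of censoring.** Section 3.1 explains early termination by the failure to quantify "plasma oxytocin using a selective and sensitive (LLQ 2pg/mL) analytical assay", owing to "low oxytocin concentrations (<2pg/mL) in the majority of samples collected from women in Third Stage Labour (TSL), following either IM or IH administration".
- **Endpoint and displays.** Section 8.1.1 lists as primary "Plasma concentration time profile for IH oxytocin and 10 I.U. IM oxytocin". Section 10.10.5 summarises it in Table 2.6, "Summary of Plasma Concentration-time Data". The only Group 1 PK figure (section 10.10.6) is "Individual Subject Plasma Concentration-time Plot (Linear and Semi-log) by Treatment".
- **PK parameters.** Section 8.1.2 expects many non-calculable values and limits the parameter summary to n, n*, median, minimum and maximum. It adds a frequency table of measurable concentrations (Table 2.8). Appendix 11, shell PK_T1, notes that "for Cmax and AUC, NCs were imputed prior to derivation of summary statistics", with Cmax set to half the LLQ, printed as 5 pg/mL.
- **Comparison.** Sections 2.1, 2.4 and 8.3.1 drop any formal inhaled-versus-IM analysis.

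**The concern.** Zero substitution does little harm when few values are NQ. Here the plan was written knowing that most are. An NQ sample is left-censored, and putting it at the lower end of its possible range can only pull a mean down. Where NQ samples are more than half of a table cell, the median becomes the imputed constant.

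The plan adapts its statistics to this problem for PK parameters but not for concentrations. With the formal comparison gone, Table 2.6 is the only display that summarises the primary profile by treatment and time. A printed median of 0 pg/mL states more than the assay can show, which is only that the value is below 2 pg/mL. The two tables also treat the same woman differently. If all her samples are NQ, she counts as 0 at every time in Table 2.6 but has a positive imputed Cmax in Table 2.7.

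**Working it through.** The plan gives no figure for this point, so there is nothing to reproduce.

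**Inputs**
- LLQ L = 2 pg/mL (section 3.1).
- NQ share p: above 50% over all samples (section 3.1). No share by arm or time is given. Assumed range: 55% to 90%.
- Distribution: log-normal, CV 50% to 150% (assumed, for illustration).

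**1. Bound without a distribution.** Zero-filled mean = true mean − p × E[C | C < L]. Because E[C | C < L] lies between 0 and 2, the mean is low by at most 2p pg/mL: 2 × 0.6 = 1.2 at 60% NQ and 2 × 0.9 = 1.8 at 90% NQ.

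**2. Median.** If p > 0.5 in a cell, the middle value is an imputed zero and the printed median is exactly 0. Over the assumed range the true medians run from 0.50 to 1.88 pg/mL.

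**3. Illustrative size.** Let σ² = ln(1 + CV²), z = Φ⁻¹(p) and μ = ln 2 − σz. Then the true mean is exp(μ + σ²/2), and the zero-filled mean is the true mean × [1 − Φ(z − σ)].

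Example, CV 100%, p = 0.70: σ = 0.833, z = 0.524, μ = 0.257. The true mean is 1.83. The zero-filled mean is 1.83 × 0.621 = 1.14, which is 38% too low.

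True mean → zero-filled mean (pg/mL):

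| CV | 55% NQ | 70% NQ | 90% NQ |
|---|---|---|---|
| 50% | 2.11 → 1.34 (−36%) | 1.75 → 0.84 (−52%) | 1.22 → 0.26 (−79%) |
| 100% | 2.55 → 1.94 (−24%) | 1.83 → 1.14 (−38%) | 0.97 → 0.32 (−67%) |
| 150% | 3.15 → 2.62 (−17%) | 2.04 → 1.45 (−29%) | 0.90 → 0.38 (−58%) |

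The absolute loss is about 0.5 to 1.0 pg/mL.

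**4. Effect on a side-by-side reading.** Difference between two arms (pg/mL, from unrounded values):

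| Arm 1 | Arm 2 | True difference in means | Zero-filled difference |
|---|---|---|---|
| 60% NQ, CV 50% | 60% NQ, CV 50% | 0.00 | 0.00 |
| 60% NQ, CV 50% | 80% NQ, CV 50% | 0.48 | 0.63 |
| 70% NQ, CV 100% | 90% NQ, CV 100% | 0.85 | 0.82 |
| 90% NQ, CV 200% | 80% NQ, CV 30% | −0.75 | −0.04 |
| 80% NQ, CV 150% | 70% NQ, CV 30% | −0.34 | +0.13 |

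(The last two rows use CVs outside the 50% to 150% range, to show what unequal spread can do.) The difference in means can stay at zero, grow, shrink or change sign. The medians behave differently: in the second and third rows, true median differences of 0.43 and 0.60 are printed as 0 against 0.

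**5. Against the Cmax rule.** With L = 2, half the LLQ is 2/2 = 1 pg/mL. The shell's 5 pg/mL implies an LLQ of 2 × 5 = 10 pg/mL, which is not the LLQ in section 3.1.

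**6. Would half-LLQ cure Table 2.6?** No. Over the assumed 55% to 90% NQ and CV 50% to 150%, its bias in the mean runs from about −12% to +43%. Above 50% NQ it prints a median of 1 in both arms, again an imputed constant.

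**The case against.** **Reach is limited.** Section 10.5.3 confines imputation to summaries and summarised graphs, so the individual plots (Figure 2.8) and the concentration listing (Listing 52) keep the data as reported. This stands: the point concerns one table.

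**NQ frequency is disclosed.** Table 2.8 counts women by how many measurable concentrations they have, and section 3.1 says openly that the primary objective cannot be met. That helps. But section 10.10.5 makes Table 2.8 an overall summary, not one by time point, so it cannot show how much of any Table 2.6 row is imputed.

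**The majority is pooled.** The schedule runs from pre-dose to 4 hours. Pre-dose and late samples could account for much of the NQ total while early post-dose times are largely quantifiable. This stands: medians of 0 follow only at times with more than half NQ, and the document does not say which times those are.

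**Sources not shown.** GUI_51487, the IDSL principle and the pkct1 shell may add rules or settle which statistics are printed. This too stands as a limit, but the RAP itself states the zero rule.

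**Stronger readings.** A reader might infer that zero-filling exaggerates any inhaled-versus-IM difference. Step 4 does not support that. The ratio of means does widen in the equal-CV cases with unequal NQ shares, but the plan computes no such ratio. A reader might also extend the point to Group 2 pre-dose (endogenous) oxytocin, because the Group 2 RAP repeats the rule. No NQ share is given there. Its sections 8.1.1.2 and 10.5.3 treat pre-dose as a derived PK parameter, for which a separate NQ standard applies, so that extension is not established.

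**Conclusion.** The point holds for the Group 1 concentration summary and should be corrected before Table 2.6 is produced. The downward bias, and the bound of 2 pg/mL times the NQ share, need only the stated LLQ and the zero rule. The zero medians also need more than half NQ at the time concerned. The 17% to 79% range rests on the assumed log-normal form, CVs and NQ shares, and on Table 2.6 printing a mean, which the referenced standard would decide.

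No direction can be claimed for the inhaled-versus-IM contrast, because NQ shares by arm and time are not given. Since the analysis is descriptive, the harm is a misleading table, not a wrong test. The conflict between zero for concentrations and half the LLQ for Cmax is plain on the page. The 5 pg/mL may be carried over from a template, but it does not fit an LLQ of 2 pg/mL.

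**What to change.** In Group 1 RAP section 10.5.2, replace the zero rule for Table 2.6 with the following:

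- At each nominal time and treatment, present n, the number and percentage NQ, median, minimum and maximum, with NQ values ranked lowest and displayed as <2 pg/mL.
- Do not print the arithmetic mean and SD where more than half of the samples are NQ.
- Elsewhere, show the mean twice, with NQ = 0 and with NQ = LLQ, as bounds. At up to 50% NQ these are at most 2 × 0.5 = 1.0 pg/mL apart.

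Also reconcile the PK_T1 footnote with the 2 pg/mL LLQ, and state how the Cmax imputation relates to the way NQ is shown in Table 2.6.

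The cost is a wording change and a small programming change, with no new data. The downside is a departure from the sponsor's default display and fewer printed means.

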3.2. Final Analyses

The final planned primary analyses for Group 1 will be performed after the completion of the following sequential steps:

1. All participants who had enrolled into the study prior to the termination of the study as defined in the protocol will be part of final analysis.
2. All required database cleaning activities have been completed for group 1 and final database release (DBR) and database freeze (DBF) for group 1 has been declared by Data Management.
3. All criteria for unblinding the randomization codes for group 1 have been met.
4. Randomization codes for group 1 have been distributed according to RandAll NG procedures.

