Reporting of No treatment	
If in a situation where a subject has received no treatment, then the subject will be included only in Screened and enrolled population.	
Graphical Displays	
Refer to IDSL Statistical Principals 7.01 to 7.13. All figures will use coloured lines	

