10.6.2. Study Population

Demographics
Age

 • GSK standard IDSL algorithms will be used for calculating age. • Randomization date will be used as reference date to calculate age
Body Mass Index (BMI)

 • Calculated as Weight (kg) / [Height (m)²
Extent of Exposure

 • Number of days of exposure to study drug will be calculated based on the formula: Duration of Exposure in Days = Treatment Stop Date – (Treatment Start Date) + 1 • Participants who were randomized but did not report a treatment start date will be categorised as having zero days of exposure. If there are any treatment breaks during the study, exposure data will be adjusted accordingly.

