10.7. Appendix 7: Reporting Standards for Missing Data

10.7.1. Premature Withdrawals

Element	Reporting Detail
General	
 • Subject study completion (i.e. as specified in the protocol) was defined as who has completed all phases of the study including the follow-up visit(s). • Withdrawn subjects may be replaced in the study. • All available data from participants who were withdrawn from the study will be listed and all available planned data will be included in summary tables and figures, unless otherwise specified.

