10.10.4. Study Population Tables

Study Population Tables					
No.	Population	IDSL / Example Shell	Title	Programming Notes	Deliverable [Priority]
Subject Disposition					
1.7.	Safety	ES1	Summary of Subject Disposition for the Subject Conclusion Record	ICH E3, FDAAA, EudraCT	DR [1], SAC
1.8.	Enrolled	NS1	Summary of Number of Subjects Enrolled by Country and Site ID	EudraCT/Clinical Operations	DR [1], SAC
Population Analysed					
1.9.	Screened	SP1	Summary of Study Populations		DR [1], SAC
Demographic and Baseline Characteristics					
1.10.	Safety	DM1	Summary of Demographic Characteristics	ICH E3, FDAAA, EudraCT	DR [1], SAC
1.11.	Enrolled	DM11	Summary of Age Ranges	EudraCT	DR [1], SAC
1.12.	Safety	DM5	Summary of Race and Racial Combinations	ICH E3, FDA, FDAAA, EudraCT	DR [1], SAC

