10.10.9. ICH Listings

ICH: Listings					
No.	Population	IDSL / Example Shell	Title	Programming Notes	Deliverable [Priority]
Subject Disposition					
35	Screened	ES7	Listing of Reasons for Screening Failure		DR [1], SAC
36.	Safety	ES2	Listing of Reasons for Withdrawal		DR [1], SAC
37.	Safety	TA1	Listing of Randomised and Actual Treatments		DR [1], SAC
Protocol Deviations					
38.	Safety	DV2	Listing of Important Protocol Deviations		DR [1], SAC
39.	Safety	IE3	Listing of Participants with Inclusion/Exclusion Criteria Deviations		DR [1], SAC
Populations Analysed					
40.	Enrolled	SP3	Listing of Participants Excluded from Analysis Population		DR [1], SAC
Demographic and Baseline Characteristics					
41.	Safety	DM2	Listing of Demographic Characteristics		DR [1], SAC
42.	Safety	DM9	Listing of Race		DR [1], SAC
Prior and Concomitant Medications					
43.	Safety	CM3	Listing of Concomitant Medications		DR [1], SAC
Exposure and Treatment Compliance					
44.	Safety	EX3	Listing of Exposure Data		DR [1], SAC
Adverse Events					
45.	Safety	AE8	Listing of All Adverse Events		DR [1], SAC
46.	Safety	AE7	Listing of Subject Numbers for Individual Adverse Events		DR [1], SAC

ICH: Listings					
No.	Population	IDSL / Example Shell	Title	Programming Notes	Deliverable [Priority]
Serious and Other Significant Adverse Events					
47.	Safety	AE8	Listing of Serious Adverse Events		DR [1], SAC
48.	Safety	AE8	Listing of Adverse Events Leading to Withdrawal from Study		DR [1], SAC
All Laboratory					
49.	Safety	LB5	Listing of All Hematology Data	All PCI criteria will be flagged	DR [1], SAC
Vital Signs					
50.	Safety	VS4	Listing of All Vital Signs Data	All PCI criteria will be flagged	DR [1], SAC

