10.10.4. Study Population Tables

Study Population Tables					
No.	Population	IDSL / Example Shell	Title	Programming Notes	Deliverable [Priority]
Subject Disposition					
1.1.	Safety	ES1A	Summary of Participant Disposition for the Participant Conclusion Record	By Cohort ICH E3, FDAAA, EudraCT	DR [1], SAC
1.2.	Enrolled	NS1	Summary of Number of Subjects Enrolled by Country and Site ID	By Cohort EudraCT/Clinical Operations	DR [1], SAC
Population Analysed					
1.3.	Screened	SP1	Summary of Study Populations	By Cohort	DR [1], SAC
Demographic and Baseline Characteristics					
1.4.	Safety	DM3	Summary of Demographic Characteristics	By Cohort ICH E3, FDAAA, EudraCT	DR [1], SAC
1.5.	Enrolled	DM11	Summary of Age Ranges	By Cohort EudraCT	DR [1], SAC
1.6.	Safety	DM5	Summary of Race and Racial Combinations	By Cohort ICH E3, FDA, FDAAA, EudraCT	DR [1], SAC

CONFIDENTIAL

205920

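### Group 1 disposition, withdrawal, randomised-versus-actual, deviation and exposure displays are run on dosed women only, so anyone enrolled or randomised but not dosed is missing from them

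*SAP*

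**What the plan says.** The SAP document holds two plans, a Group 1 RAP (women in the third stage of labour) and a Group 2 RAP (non-pregnant women).

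In the Group 1 RAP, Section 4 makes Safety depend on at least one dose. Enrolled takes in everyone who passed screening and entered the study, including all who were randomised. Section 10.5.2 draws the consequence: "If in a situation where a subject has received no treatment, then the subject will be included only in Screened and enrolled population".

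Section 10.10.4 assigns Table 1.7, "Summary of Subject Disposition for the Subject Conclusion Record", to Safety. Section 10.10.9 assigns to Safety Listing 36, "Listing of Reasons for Withdrawal", Listing 37, "Listing of Randomised and Actual Treatments", both deviation listings (38 and 39) and the exposure listing (44).

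Other statements in the same RAP reach wider:

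- Section 10.6.2: "Participants who were randomized but did not report a treatment start date will be categorised as having zero days of exposure".
- Section 4.1 undertakes to list every inclusion/exclusion deviation recorded on the eCRF eligibility page.
- Section 10.7.1: "All available data from participants who were withdrawn from the study will be listed". The sentence goes on to cover summaries and ends with a proviso allowing other specifications.
- Section 3.2 (one closing word omitted): "All participants who had enrolled into the study prior to the termination of the study as defined in the protocol will be part of final".

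The Group 2 RAP follows the same pattern. Table 1.1, "Summary of Participant Disposition for the Participant Conclusion Record", and Listings 2 to 5 and 10 are on Safety.

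**The concern.** A disposition table exists to account for everyone who entered the study and to show where and why they left. A listing of randomised against actual treatment exists partly to show who was randomised and then not treated. If both are restricted to treated women, the first leaves out every loss before dosing. The second can show a switch of treatment but never a randomised woman who received nothing. Eligibility deviations have the same problem: a woman found ineligible after enrolment, and not dosed for that reason, is a case the listing should contain.

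What is at stake is complete accounting. Table 1.7 is marked for ICH E3, FDAAA and EudraCT, so an incomplete count would go into public reporting. Group 1 was also terminated early (Section 3.1), so women enrolled but not yet dosed at that point are a foreseeable group.

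**Working it through.** The plan gives no figure to reproduce. The check compares the population rules with the population column of each Group 1 display.

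**Step 1: who is affected.** Take a woman who passed screening and entered the study but received no study drug. By Sections 4 and 10.5.2 she is in Screened and Enrolled, and not in Safety. She is not in PK either, because PK is a subset of Safety.

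**Step 2: where she should appear but cannot.**

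| Display | Content | Population | Can include her? |
|---|---|---|---|
| Table 1.7 | Disposition | Safety | No |
| Listing 36 | Withdrawal reasons | Safety | No |
| Listing 37 | Randomised and actual treatment | Safety | No |
| Listing 38 | Important deviations | Safety | No |
| Listing 39 | Eligibility deviations | Safety | No |
| Listing 44 | Exposure | Safety | No |

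**Step 3: where she can still appear.**

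| Display | Content, by title | Population |
|---|---|---|
| Table 1.8 | Numbers by country and site | Enrolled |
| Table 1.9 | Study populations | Screened |
| Table 1.11 | Age ranges | Enrolled |
| Listing 40 | Exclusion from an analysis population | Enrolled |

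Listing 35 is on Screened but covers screening failures, and she passed screening. So six displays exclude her and four admit her. By title, none of the four gives a withdrawal status or reason.

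**Step 4: effect on the plan's other statements.**

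- *Zero-exposure rule (10.6.2).* The only Group 1 exposure display is Listing 44, on Safety. The women the rule describes cannot be in it, so the rule never takes effect.
- *All eligibility deviations (4.1).* Listing 39 on Safety cannot contain an undosed woman's deviation, so the commitment is not met.
- *Withdrawn participants' data (10.7.1).* The proviso lets the display list specify otherwise. This is a tension only.

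**Step 5: direction of the effect on Table 1.7.** Let E be the number enrolled, U the enrolled but undosed, and W the dosed women who do not complete. Section 10.7.1 defines completion as finishing all study phases including follow-up, so every undosed woman is a non-completer.

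- Proportion not completing, on Safety: W/(E − U)
- Proportion not completing, on Enrolled: (W + U)/E
- Enrolled minus Safety: U(E − U − W) / [E(E − U)]

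E − U − W is the number of dosed completers, so the difference is never negative. It is positive whenever at least one woman is undosed and at least one dosed woman completes. The direction is therefore fixed. The size is not, because the document gives neither E nor U.

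**Step 6: Group 2.** Table 1.1 and Listings 2 to 5 and 10 are on Safety, and the Group 2 RAP repeats the zero-exposure rule (10.6.2) and the eligibility-deviation commitment (4.1). However, its Section 10.5.2 has its own table for a partial dose or no treatment in a given period. That table keeps such women in listings and in study population tables without period treatment. It covers a woman who missed one session. It does not clearly cover one who was never dosed and so is not in Safety at all.

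**The case against.** The strongest reply is that the choice is declared. Section 4 says Safety serves study population as well as safety displays, and Section 6.1 names both Safety and Enrolled for that purpose. Group 1 reporting is descriptive, with no formal comparison of inhaled and intramuscular oxytocin, so losses before dosing bias no planned contrast. The display templates are sponsor-library shells that are not reproduced, so what Listing 40 carries can be judged only by its title. All of this stands. It limits the consequence, but it does not put the missing women into the disposition or withdrawal displays.

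Several stronger readings are tempting, and the document does not support them:

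- *Undosed women vanish from the report.* They do not. Table 1.9 and Listing 40 still show them as enrolled and excluded.
- *Sections 10.7.1 and 3.2 are flatly contradicted.* The first carries its proviso. The second is a step listed before the final analysis and promises no particular display.
- *The screening window of up to 168 days implies heavy or arm-dependent loss after randomisation.* That interval runs from screening to dosing. The RAP places randomisation between screening and administration without timing it, so the randomisation-to-dosing window is unknown.
- *Moving to Enrolled recovers every early loss.* Women screened but never enrolled are outside Enrolled too.
- *Group 2 has the identical fault.* Its own no-treatment table means the point carries over only for never-dosed women.

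**Conclusion.** The point holds as a reporting gap. Followed as written, the Group 1 plan leaves every enrolled or randomised but undosed woman out of the disposition counts, withdrawal reasons, randomised-versus-actual listing, both deviation listings and the exposure listing. It conflicts with the zero-exposure rule and with the commitment to list all eligibility deviations. Section 10.5.2 is not at fault; the population columns in Sections 10.10.4 and 10.10.9 are.

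The number of women affected is not stated and cannot be derived. If there are none, nothing is lost. If there are some, Table 1.7 understates non-completion, assuming it reports proportions of its own population. A reader might infer biased PK or safety results, but those displays properly use dosed women and none of their estimates changes. The conclusion also assumes that the unseen shells hold what their titles say. The correction should be made because it is cheap and makes the participant accounting complete.

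**What to change.** In the Group 1 RAP, change the population of Table 1.7 and Listings 36, 37, 38, 39 and 44 from Safety to Enrolled. Show randomised, undosed women under their assigned arm as a separate category, with the reason. Show women enrolled but not randomised in the total only. State this as an exception to the rule in Section 10.5.2 that data are reported by treatment actually received, since an undosed woman has none. Keep Safety for adverse event, laboratory and vital-sign displays.

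In the Group 2 RAP, relabel Table 1.1 and Listings 2 to 5 and 10 in the same way for never-dosed women only. Leave the existing handling of a single untreated period as it is.

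The cost is six label changes in Group 1, six in Group 2 (Table 1.1, Listings 2, 3, 4, 5 and 10), and a not-dosed category in the disposition layout. No new population definition is needed, and no new data collection should be. Reported withdrawals may look less favourable.
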